We will use the ultrasound pulse parameters used by Cain et al ³⁹ for sonication of the globus pallidus (see previous paragraph) because their experiment demonstrated hemodynamic effects without adverse effects in healthy subjects and the stimulation parameters were very low-intensity and extremely low risk. If we do not see effects on functional connectivity or symptoms after the first 5 participants and if the single sessions are well-tolerated, we will switch to repeated dosing, applying three PLIFUS or sham sonifications over 5 days since repeated exposures may be required to produce detectable effects. A single session of PLIUS will include 5 minutes net total dosage of PLIFUS. The exposure uses ten 30 sec blocks of PLIFUS sonication with 30 sec rests in-between spread over ten minutes. Sonication will be delivered (Fig. 3) in low-amplitude pulses using a carrier wave frequency: 361 kHz, pulse repetition frequency: 100 Hz, and duty cycle: 5 % yielding an I_{spta} 1.5 W/cm² at the Gpi. The acoustic intensity used is in the range of FDA and Electrotechnical Technical Commission (ETC) regulation standards for diagnostic and therapeutic ultrasound, respectively ²⁸.

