2.4.2 Known Potential Benefits

No known potential benefits are associated with a single administration of PLIFUS in individuals with schizophrenia. Results of this study may lead to the development of a new therapeutic approach for psychotic symptoms that do not respond to currently available treatments.

3 Objectives and Purpose

The overall purpose of this study is to determine feasibility and tolerability of PLIFUS sonication of the right Gpi in individuals with schizophrenia and to determine whether a single session of PLIFUS sonication will decrease Gpi functional connectivity and decrease intensity of hallucinations and delusions compared to sham sonication. This pilot study will allow us to determine whether the proposed target and PLIFUS sonication parameters produce detectable changes in our imaging biomarkers in order to demonstrate target engagement and to determine whether

we can detect a signal suggestive of therapeutic efficacy to justify future therapeutic trials. If a single session of PLIFUS does not produce measurable effects in the first 12 completers with good quality imaging data, we will administer 3 sessions of PLIFUS and of sham, each over 5 days, in 4 additional participants.

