3.2 Secondary Objectives

If the primary objective is not successful, we will test the hypothesis that 3 sessions of PLIFUS targeting the right Gpi administered over 5 days will produce a decrease in Gpi functional connectivity and a reduction in symptoms compared to sham.

4 Study Design and Endpoints

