A study psychiatrist will be present during all sessions of PLIFUS and sham. Participants will be monitored during and after sonication until psychiatrically cleared by the study psychiatrist 1 hour after completion of each session. Participants will be contacted 24-48 hours and 7 days after each treatment period and symptoms, side effects and suicidality assessed.

9 Statistical Considerations

This is a pilot study intended to obtain preliminary data to guide future studies. The analysis will primarily be descriptive for this purpose and, due to the small sample size, effect sizes will be the primary signal of target engagement. Consistent with other studies in the field, we have selected an effect size of 0.5 as our threshold. In addition, there is a pre-planned review of results after completion of the first 5 participants; the administration of PLIFUS/sham will be increased from one session to three sessions over 5 days if an effect size of 0.5 or greater with PLIFUS is not detected in change from baseline in GPi functional connectivity or symptom response compared to sham.

The primary statistical analysis will be performed in completers without imputation of missing data and will be change in primary outcomes (GPi functional connectivity and symptom severity) from baseline to the first measure post-sonication or sham (immediately post-sonication for symptoms; 10-30 minutes for fMRI). PLIFUS and sham PLIFUS will be compared using a linear mixed effects model with baseline measures (GPI functional connectivity and severity of psychotic symptoms) as continuous variables; treatment (PLIFUS or sham) and sequence as categorical variables; and participant as a random effect. Similar secondary exploratory analyses will be performed at additional time points (symptom severity during sonication, 60 minutes, 1 day and 7 days after sonication). Secondary analyses of other outcome measures (BPRS total score, PSYRATS and CGI) will be analyzed following the same approach. Safety measures, including the SAFTEE and C-SSRS will be summarized descriptively. If the study design is adapted (sonication increased to 3 sessions) after the first 12 completers with good quality imaging data, results from the first 12 completers and subsequent 4 participants will be analyzed separately.

Sample Size

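### The four-person, three-session stage cannot support the adjusted mixed model, and the plan has no three-versus-one estimate to set against the 0.5 cut-off; add one exploratory contrast

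*Combined protocol and SAP*

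**What the plan says.** Section 9 specifies a "linear mixed effects model with baseline measures (GPI functional connectivity and severity of psychotic symptoms) as continuous variables", with "treatment (PLIFUS or sham) and sequence as categorical variables; and participant as a random effect". The outcome is the change "from baseline to the first measure post-sonication or sham". If sonication is increased to three sessions, "results from the first 12 completers and subsequent 4 participants will be analyzed separately". The document contains no session-number term, pooled model or three-versus-one contrast.

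Section 3 describes the added stage: "we will administer 3 sessions of PLIFUS and of sham, each over 5 days, in 4 additional participants". Section 2.1.4 gives its reason: "since repeated exposures may be required to produce detectable effects". Section 3.2 and objective 5 of the Protocol Summary ask only whether three sessions do better than sham.

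On the threshold, Section 9 says "we have selected an effect size of 0.5 as our threshold". The Protocol Summary uses 0.5 as the general threshold for signal detection. Sections 6.1.8 and 7.15 use a result below 0.5 in the first 12 to open the three-session stage.

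**The concern.** Two things are at stake if the stage opens.

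1. **The adjusted three-session estimate.** A model suited to 12 crossover participants has almost no residual information in 4. Its adjusted effect would carry an interval too wide to use.
2. **The comparison readers will make.** The stage exists because one session may be too little, yet the plan supplies no estimate of three versus one. What is left is a result below 0.5 in the 12 set beside a result above or below 0.5 in the 4. The stage opens only after a low first result, so this comparison leans towards three sessions even when the true effects are equal. Section 9 says the data are meant to guide future studies, and a choice between single and repeated sessions is one that they could be used for.

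**Working it through.** The plan has no power calculation or precision target to reproduce. Alpha, SD and the standardiser of the effect size are not stated. I assume two-sided 95% intervals, normal data and, unless noted, effects in SDs of the within-person PLIFUS-minus-sham difference, signed so that positive is favourable.

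**Step 1: parameters against data.** Section 3 and the crossover statement in Section 7.4 imply that each of the 4 receives both conditions, giving 4 × 2 = 8 changes from baseline.

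- Both baselines in each model: intercept 1 + baselines 2 + treatment 1 + sequence 1 + participant variance 1 + residual variance 1 = 7.
- Only the outcome's own baseline: 6.

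Treatment is estimated within participants. Sequence drops out of the 4 paired differences, leaving the treatment effect and the baseline slopes. Residual df are 4 − 3 = 1 with two baselines, 4 − 2 = 2 with one, and 4 − 1 = 3 with none.

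**Step 2: precision of the three-session effect.** At unit SD and without covariate losses, the half-width is t/√4:

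- 1 df: 12.71/2 = 6.35
- 2 df: 4.30/2 = 2.15
- 3 df: 3.18/2 = 1.59

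Simulated median half-widths, which allow for estimating the SD and the slopes:

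| Baselines | 4 alone | Joint model of all 16 |
|---|---|---|
| two | about 6.7 (6.4 to 6.7 across runs) | 1.14 |
| one | about 2.1 | 1.09 |
| none | 1.4 | 1.04 |

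The two-baseline figure comes from regression on paired differences. A random-participant model would recover a little between-person information on the slopes. In 400 null fits of the mixed model at n = 4, a Wald z test rejected 26% (two baselines) or 23% (one) of the time, against 7–8% at n = 12.

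**Step 3: the side-by-side reading under equal effects.** For true paired effect δ, the observed effect size times √n follows a noncentral t:

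- P(12 below 0.5) = P(T with 11 df, noncentrality δ√12, < 0.5√12)
- P(4 at least 0.5) = 1 − P(T with 3 df, noncentrality 2δ, < 1)

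The stages are independent given δ, so the two multiply.

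| True effect in both stages | 12 below 0.5 | 4 at least 0.5 | Both |
|---|---|---|---|
| 0 | 0.944 | 0.196 | 0.185 |
| 0.2 | 0.826 | 0.315 | 0.260 |
| 0.3 | 0.730 | 0.384 | 0.280 |
| 0.4 | 0.613 | 0.457 | 0.280 |
| 0.5 | 0.485 | 0.531 | 0.257 |

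The third column is also the chance of the pattern once the stage has opened. Standardising by the change-score SD instead (correlation between conditions 0 to 0.7, true effect 0 to 0.4) gives 13–28%. Section 7.15 names four measures. Requiring all four below 0.5 in the 12 and any at or above 0.5 in the 4 gives 36–46% at a true effect of 0 (correlation between measures 0 to 0.6).

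**Step 4: what a direct contrast gives.** SE = √(1/12 + 1/4) = 0.577 SD. With t(14) = 2.145, the half-width is 2.145 × 0.577 = 1.24 SD. Power is about 13% for a true difference of 0.5 SD and 36% for 1.0 SD; 80% power needs about 1.74 SD. If a claim for three sessions requires this interval to lie above zero, the false reading falls from 26–28% to about 2%, under equal effects and equal variances. The trigger still biases the estimate: with no real difference, the 4 exceed the 12 by 0.09 to 0.22 SD on average at true effects of 0.2 to 0.5.

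**The case against.** - **A reader might infer that fitting the stages separately creates the false dose reading.** It does not. If the three-session effect is standardised by an SD pooled over all 16, the pattern still occurs in 23%, 25% and 24% of trials at true effects of 0.2, 0.3 and 0.5. Only the added contrast addresses it.
- **A reader might infer that the trial plans to conclude that three sessions work where one did not.** No section says so. Three versus one is not a stated objective, and 0.5 is not set as a decision rule for the 4. The documents support only the narrower statement that the results can be read that way and that nothing guards against it.
- **The study declares itself exploratory.** The Protocol Summary, Section 9 and Section 7.15 (DSMB decisions without statistical tests) all say so. This limits the severity. It does not help the reader of an effect size from 4 people, and effect sizes are the plan's chosen signal.
- **The 7-parameter count takes the less favourable reading.** The baseline list mirrors the two primary outcomes, so one baseline per model is at least as natural; the relevant half-width is then about 2.1 SD. Section 9 also does not say outright that the mixed model is refitted to the 4. Both points stand, but 2.1 SD is still very wide and no alternative analysis is given.
- **Separate analysis is defensible, and pooling has costs.** Stage is not randomised, and three sessions over 5 days may produce different variability. If the stage-2 SD is 1.5 or 2 times larger, the pooled nominal 95% interval for the three-session effect covers about 87% or 80%. The joint model should therefore not replace the separate results.

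**Conclusion.** The point holds as a modest one, worth considering. A refit of the stated model to 4 participants gives an adjusted estimate that is almost uninformative: about 2.1 SD with one baseline and 6.7 SD with both, against 1.4 SD unadjusted. The missing three-versus-one estimate leaves only the 0.5 cut-off in each stage, and that comparison favours three sessions falsely in about 26–28% of trials at equal true effects of 0.2 to 0.5 on one measure. The direct contrast would not be precise; its value is to show that 16 participants cannot separate the two schedules unless the difference is very large.

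These figures assume normal data, the crossover reading of the added stage (the Protocol Summary and Section 4.1 are looser, and a parallel reading would leave 4 values), and 12 completers in stage 1. Section 2.1.4 and the opening of Section 9 place the switch review after 5 participants, whereas the other sections, including the end of Section 9, say 12. These must be reconciled because the stage-1 sample size depends on them.

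**What to change.** In Section 9:

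1. Keep the separate 12-completer analysis as the single-session result.
2. For the 4, report the individual and mean PLIFUS-minus-sham differences descriptively, and do not rely on the fully adjusted model alone.
3. Add one exploratory mixed model of all 16 with stage, treatment and treatment-by-stage. Report the three-minus-one difference with its 95% interval.
4. State that any claim that three sessions do more than one rests on that interval and not on the 0.5 cut-off in each stage, and that the stage opened only after a low first result.
5. Beside the joint model, show a version with stage-specific residual variance or the unpooled differences, because the joint model assumes similar variance and baseline slopes in both stages.
6. Reconcile the review after 5 with the review after 12.

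The cost is a few sentences and one extra model, with no added participants, visits or measurements. The price is the shared-variance and shared-slope assumption, which item 5 exposes.

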9.1 Measures to Minimize Bias

9.1.1 Enrollment/Randomization/Masking Procedures

Because this is a cross-over study, the primary concern with randomization imbalance is with an order effect. We will examine this possibility statistically. The sham condition consists of an identical procedure during which the sonication equipment produces an identical noise. We believe this will fully mask the treatment condition but will ask participants after each session which condition they believe they received and will analyze these results to verify the success of our masking.

9.1.2 Evaluation of Success of Blinding

Participants and symptom raters will be asked whether they believe the participant received PLIFUS or sham after each intervention session. The results of these queries will be analyzed and reported.

9.1.3 Breaking the Study Blind/Participant Code

The study blind will only be broken in the case of an unexpected serious adverse event. This decision will be made by [name] in an emergency; if not an emergency, it will first be discussed with the Chair of the DSMB, [name].

10 Source Documents and Access to Source Data/Documents

Source data is all information, original records of clinical findings, observations, or other activities in a clinical trial necessary for the reconstruction and evaluation of the trial. Source data are contained in source documents. Examples of these original documents, and data records include: hospital records, clinical and office charts, laboratory notes, memoranda, subjects' diaries or evaluation checklists, pharmacy dispensing records, recorded data from automated instruments, copies or transcriptions certified after verification as being accurate and complete, microfiches, photographic negatives, microfilm or magnetic media, x-rays, subject files, and records kept at the pharmacy, at the laboratories, and at medico-technical departments involved in the clinical trial. It is acceptable to use CRFs as source documents.

The study case report form (CRF) is the primary data collection instrument for the study. All data requested on the CRF must be recorded. All missing data must be explained. If a space on the CRF is left blank because the procedure was not done or the question was not asked, write "N/D". If the item is not applicable to the individual case, write "N/A". All entries should be printed legibly in black ink. If any entry error has been made, to correct such an error, draw a single straight line through the incorrect entry and enter the correct data above it. All such changes must be initialed and dated. DO NOT ERASE OR WHITE OUT ERRORS. For clarification of illegible or uncertain entries, print the clarification above the item, then initial and date it.

Access to study records will be limited to IRB-approved members of the study team. The investigator will permit study-related monitoring, audits, and inspections by the IRB/EC, the sponsor, government regulatory bodies, and University compliance and quality assurance groups of all study related documents (e.g. source documents, regulatory documents, data collection instruments, study data etc.). The investigator will ensure the capability for inspections of applicable study-related facilities (e.g. pharmacy, diagnostic laboratory, etc.).

11 Quality Assurance and Quality Control

[name] will meet with the study team weekly to review procedures and documentation.

12 Ethics/Protection of Human Subjects

12.1 Ethical Standard

The investigator will ensure that this study is conducted in full conformity with Regulations for the Protection of Human Subjects of Research codified in 45 CFR Part 46, 21 CFR Part 50, 21 CFR Part 56, and/or the ICH E6.

12.2 Institutional Review Board

The protocol, informed consent form(s), recruitment materials, and all participant materials will be submitted to the IRB for review and approval. Approval of both the protocol and the consent form must be obtained before any

participant is enrolled. Any amendment to the protocol will require review and approval by the IRB before the changes are implemented to the study. All changes to the consent form will be IRB approved; a determination will be made regarding whether previously consented participants need to be re-consented.

12.3 Informed Consent Process

12.3.1 Consent/Accent and Other Informational Documents Provided to Participants

Consent forms describing in detail the study agent, study procedures, and risks are given to the participant and written documentation of informed consent is required prior to starting intervention/administering study product. The following consent materials are submitted with this protocol;

- Form for documenting capacity to sign informed consent
- 10 item quiz to document participant understanding of key aspects of participation
- Informed Consent Form
- Key Information Sheet

12.3.2 Consent Procedures and Documentation

Informed consent is a process that is initiated prior to the individual's agreeing to participate in the study and continues throughout the individual's study participation. Extensive discussion of risks and possible benefits of participation will be provided to the participants and their families. Consent forms will be IRB-approved and the participant will be asked to read and review the document. The investigator will explain the research study to the participant and answer any questions that may arise. All participants will receive a verbal explanation in terms suited to their comprehension of the purposes, procedures, and potential risks of the study and of their rights as research participants. In addition, the potential subject must also achieve a perfect score on a ten-item true/false quiz that asks questions about the study procedures and potential risks. Participants will have the opportunity to carefully review the written consent form and ask questions prior to signing. The participants should have the opportunity to discuss the study with their surrogates or think about it prior to agreeing to participate. The participant will sign the informed consent document prior to any procedures being done specifically for the study. The participants may withdraw consent at any time throughout the course of the trial. A copy of the signed informed consent document and key information sheet will be given to the participants for their records. The rights and welfare of the participants will be protected by emphasizing to them that the quality of their medical care will not be adversely affected if they decline to participate in this study.

A copy of the signed informed consent document will be stored in the subject's research record. The consent process, including the name of the individual obtaining consent, will be thoroughly documented in the subject's research record. Any alteration to the standard consent process (e.g. use of a translator, consent from a legally authorized representative, consent document presented orally, etc.) and the justification for such alteration will likewise be documented.

For inpatients and outpatients, consent can take place remotely, in which a study team MD will review the consent form with the participant over WebEx. Participants will be provided an IRB-approved REDCap electronic consent form to sign, and a copy will be sent to their email.

12.4 Participant and Data Confidentiality

Information about study subjects will be kept confidential and managed according to the requirements of the Health Insurance Portability and Accountability Act of 1996 (HIPAA). Those regulations require a signed subject authorization informing the subject of the following:

- What protected health information (PHI) will be collected from subjects in this study
- Who will have access to that information and why
- Who will use or disclose that information
- The rights of a research subject to revoke their authorization for use of their PHI.

In the event that a subject revokes authorization to collect or use PHI, the investigator, by regulation, retains the ability to use all information collected prior to the revocation of subject authorization. For subjects that have revoked authorization to collect or use PHI, attempts should be made to obtain permission to collect at least vital status (i.e. that the subject is alive) at the end of their scheduled study period.

Participant confidentiality is strictly held in trust by the participating investigators and their staff. This confidentiality covers clinical information relating to participants. Therefore, the study protocol, documentation, data, and all other information generated will be held in strict confidence. No information concerning the study or the data will be released to any unauthorized third party.

The IRB may inspect all documents and records required to be maintained by the investigator, including but not limited to, medical records (office, clinic, or hospital).

The study participant's contact information will be securely stored for internal use during the study. At the end of the study, all records will continue to be kept in a secure location for as long a period as dictated by local IRB and Institutional regulations.

Study participant research data, which is for purposes of statistical analysis and scientific reporting, will be stored at NYU Langone Medical Center. This will not include the participant's contact or identifying information. Rather, individual participants and their research data will be identified by a unique study identification number. Data used for statistical analysis, including imaging analysis, will be de-identified. The study data entry will be secured and password protected. At the end of the study, all study databases will be de-identified and archived at the NYU Langone Medical Center.

13 Data Handling and Record Keeping

